Since the QIDS-SR16 score itself is repeatedly measured over time, a linear mixed-effects model will be applied to estimate its trajectories of the two groups during the acute treatment phase. The model will include measurement time, treatment group, their interaction, and site as fixed effects, and a Gaussian random intercept at the patient level. Baseline patient characteristics with statistically significant differences between the two groups may be also included as fixed effects if deemed necessary. The covariance matrix of the repeated measurements within each patient will be selected from the candidates of compound symmetric, first-order autoregressive (AR1), Toeplitz, and unstructured structures using the information criterion. Least-square estimates will be derived to estimate the QIDS-SR16 mean at each visit by group, and corresponding linear contrasts can be used for group comparison at each visit. Since the responders will be further followed at months 1, 3 and 6 after the acute phase, another linear

mixed-effects model with the same formation will be applied to the subgroup of responders for their longitudinal QIDS-SR-16 data until the end of the follow up phase. The model for the change of QIDS-SR-16 score will include the score changes as the dependent variable and further include the baseline QIDS-SR-16 score as a covariate. For the other continuous secondary endpoints measured longitudinally, their analyses will follow the analysis of the QIDS-SR-16 score. These endpoints include various patient and clinician rated scales for depression, suicidality, and cognitive function (e.g., MADRS and YMRS).

For the cross-sectional endpoints such as the MoCA rating assessed at the end of treatment visit, linear regression will be used to analyze and compare the data between the two groups. Generalized linear regression (e.g., logistic regression or ordinal logistic regression) will be applied to binary or multi-categorical outcomes, depending on the variable type of the outcome.

Analysis of safety endpoints. Mortality will be summarized as percentage by group, and the chi-squared test will be used to compare the mortality rates between the two groups. If the expected number of deaths is small, the Fisher's exact test will be used instead. The other dichotomous safety outcomes such as the unexpected adverse events, adverse events causing treatment discontinuation and serious adverse events will be analyzed in the same manner.

For the vital signs including BMI, blood pressure and heart rate, the linear mixed-effect models will be applied to estimate their least-square means over time by group.

Subgroup analyses. Multiple *subgroup analyses* will be performed in order to determine whether there is heterogeneity of treatment effect due to demographic and clinical risk factors. The predefined subgroups include: psychiatric comorbidity, depression subtype, gender, race, age, treatment resistance (Stage IV-V vs other) and prior history of ECT treatment. For each subgroup analysis, we will test the interaction using the Breslow-Day test. Recognizing that the power to detect significant interactions will be low, all subgroup analyses are thus considered to be hypothesis generating.

Missing data. The missing primary endpoints will be imputed as described in the section of analysis of primary endpoint. Regarding the missing data in the secondary endpoints, the mixed-effects models or the generalization regression models implicitly assume data missing at random. We will also perform sensitivity analyses if needed. The first sensitivity analysis will be imputation.

If the endpoints are longitudinal and have mixed variable types, the set of longitudinal data will be arranged chronologically. The results are then summarized using Rubin's rule. Another sensitivity analysis will be using the pattern mixed modeling if the missingness is considered non-ignorable (i.e., missing not at random).

Sample size justification. For the outcome measure of QIDS-SR16 in TRD patients in standard anti-depressant analyses, an overall response rate of 47% was reported in the STAR*D study [1]. Zarate et al. showed that a 71% response rate of ketamine on HAMD-21 was associated with patients with major depression [2]. Murrough et al. reported a 64% response rate of ketamine on MADRS in patients with TRD [3]. Other studies revealed response rates of ketamine ranging from 50% to 90% in patients with TRD [4-14]. Janicak et al. reported a 56% response rate of ECT on HAMD-24 in patients of major depression [15]. Our preliminary internal data showed 45.8% patients as responders in the ketamine group, and 45.1% patients as responders in the ECT group, using clinician rated MADRS scales. The patients in the ketamine group were resistant to ECT treatment and still had a comparable response rate as ECT. For the ELEKT-D study, patients do not have to be ECT resistant, and hence the ketamine response rate is expected to be even higher. Based on the above data from the previous studies and our pilot study, we assume a 50% response rate for ECT patients. At a non-inferiority margin of 10% (i.e. response rate of ketamine is at most 10% lower than ECT) and a one-sided alpha value of 0.025, a total sample of 346 is needed to provide 80% power using the Farrington-Manning score test of risk difference if the actual difference is +5% (i.e. response rate of ketamine is 5% higher than ECT). If the actual difference is +10%, the statistical power would increase to 96.4% with the same sample size; if the non-inferiority margin is reduced to 5%, then the power will be 80.3%. Assuming an attrition rate of 15%, a total number of 400 subjects (200 per treatment group) are then required.

References

[2] Zarate CA Jr., Singh JB, Carlson PJ, et al. A randomized trial of an N-methyl-D-aspartate antagonist in treatment-resistant major depression. Arch Gen Psychiatry. 2006; 63(8):856–864.

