4.2 Secondary Outcomes

Other patient and clinician rated scales will be used as secondary outcome measurements. (See Table 1.)

All scales (except CADSS and BPRS) will be administered prior to treatment. CADSS and BPRS will be administered by the research nurse or a clinician post treatment. Questionnaires will be administered according to the schedule of events.

During the follow-up visits, data analysis for the Month 1, Month 3, and Month 6 visits will be conducted using the End of Treatment Visit as baseline.

5. Subject Selection

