6.2.2 Non-Responders

Patients who have less than a 50% decrease in QIDS-SR-16 score from the Baseline/Visit 1 to the EOT Visit will be classified as non-responders. These patients will not be seen for follow-up visits. However, these patients will receive a follow-up phone call one month after the End of Treatment Visit to ask about AEs/SAEs, treatment with ECT, ketamine, psychotropic medications, and complete the PGI-S and PGI-I, QIDS and MADRS assessments. Patients will be referred to their clinical provider for ongoing treatment of depression. Continuity of care between study staff and clinical providers will be carefully managed in order to provide optimal ongoing psychiatric care for the patient.

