7.5.1.1 Month 1 Follow-Up Visit (+/- 2 weeks)

- Update Medical History
- Update Psychiatric Medication Log
- Update Somatic Therapies Log
- Vitals (BP, heart rate, weight)
- Evaluation for Adverse Events or Serious Adverse Events
- Psychiatric Evaluation
- Patient Rated Behavioral Scales
 - QIDS-SR-16 (to be completed first)
 - o GSE-MY
 - o SMCQ
 - o PGI-S & PGI-I
 - o QOLS
 - o PRISE
 - o CPFQ
- Clinician Rated Behavioral Scales
 - MADRS
 - o CSSRS
 - o YMRS
 - o BPRS
 - o CGI-S & CGI-I
 - CADSS
- Cognitive Assessments

- o MoCA
- o COWAT
- o HVLT-R
- o Stroop

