7.5.2 Follow-Up Phone Call for Non-Responders

7.5.2.1 Month 1 Follow-Up Phone Call (+/- 2 weeks)

- Evaluation for Adverse Events or Serious Adverse Events
- Evaluation for additional ECT, ketamine, psychotropic treatment(s) performed
 - o Update Somatic Therapies Log
 - Update Psychiatric Medications Log
- Patient Rated Behavioral Scale
- PGI-S & PGI-I
- Completion of QIDS
- Completion of MADRS

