PGI-S			X	X	X	X	X	X	X
PGI-I				X	X	X	X	X	X
QOLS			X	X	X	X	X	X	X
PRISE			X	X	X	X	X	X	X
CPFQ			X	X	X	X	X	X	X
Treatment Preference									X
Clinician Rated Scales									
MADRS	X		X	X	X	X	X	X	X
CSSRS			X	X	X	X	X	X	X
YMRS	X		X	X	X	X	X	X	X
BPRS*			X	X	X	X	X	X	X
CGI-S**			X	X	X	X	X	X	X
CGI-I**				X	X	X	X	X	X
CADSS*			X	X	X	X	X	X	X
Cognitive Assessments									
MoCA	X								X
COWAT			X						X
HVLT-R			X						X
Stroop			X						X
NAART			X						

^{*}CADSS and BPRS to be administered post treatment.
**CGI-S and CGI-I to be performed by psychiatrist.

Schedule of Events (Follow-Up Phone Call – Non-Responders)

Visit	Month 1 (+/- 2 weeks)
Evaluate for AEs/SAEs	X
Evaluate for additional ECT, ketamine, psychotropic treatment(s)	X
Patient Rated Scales: PGI-S & PGI-I	X
Complete QIDS Form	X
Complete MADRS Form	X

Schedule of Events (Follow-Up Visits – Responders will occur through Month 1 Follow-Up at a minimum)

•	Month 1	Month 3	Month 6
Visit	(+/- 2 weeks)	(+/- 2 weeks)	(+/- 2 weeks)
Update Medical History	X	X	X
Vitals (BP, heart rate, weight)	X	X	X
Psychiatric Evaluation	X	X	X
Psychiatric Medication Log	X	X	X
Somatic Therapies Log	X	X	X
Evaluate for AEs/SAEs	X	X	X
Patient Rated Scales			
QIDS-SR-16	X	X	X
GSE-MY	X	X	X
SMCQ	X	X	X
PGI-S & PGI-I	X	X	X
QOLS	X	X	X
PRISE	X	X	X
CPFQ	X	X	X
Clinician Rated Scales			
MADRS	X	X	X
CSSRS	X	X	X
YMRS	X	X	X
BPRS	X	X	X
CGI-S & CGI-I*	X	X	X
CADSS	X	X	X
Cognitive Assessments			
MoCA	X	X	X
COWAT	X	X	X
HVLT-R	X	X	X
Stroop	X	X	X

^{*}To be performed by psychiatrist.

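### For QIDS-SR-16 and the scales that follow it, the SAP's follow-up model compares arms only among end-of-treatment responders, and no Month 1 comparison by randomised arm pools both response groups

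*SAP*

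**What the plan says.** **Follow-up efficacy.** In the SAP, Analysis of secondary endpoints, the acute-phase QIDS-SR-16 model has terms for time, arm, their interaction and site, and allows arm contrasts at each visit. For follow-up it specifies a second model: a "mixed-effects model with the same formation will be applied to the subgroup of responders for their longitudinal QIDS-SR-16 data until the end of" that phase. The same formation carries the arm terms over, so this is an arm comparison. The SAP then adds: "For the other continuous secondary endpoints measured longitudinally, their analyses will follow the analysis of the QIDS-SR-16 score". The SAP's Summary of the Changes says that version 2 has separate follow-up models for responders and non-responders. The body describes only the responder model. I do not count that difference as an error.

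**Baseline for follow-up.** Protocol 4.2 states that "data analysis for the Month 1, Month 3, and Month 6 visits will be conducted using the End of Treatment Visit as baseline".

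**What is collected at Month 1.** Under Protocol 6.2.2, non-responders are phoned and "complete the PGI-S and PGI-I, QIDS and MADRS assessments". Protocol 7.5.2.1 lists "Completion of QIDS" and of the MADRS. Responders have the same four scales at a clinic visit (Protocol 7.5.1.1), and the heading of the follow-up Schedule of Events reads "Responders will occur through Month 1 Follow-Up at a minimum". Non-responders are not contacted after Month 1 (Protocol 3), and their call does not include QOLS or cognitive tests.

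**Safety.** Protocol 8.3 collects serious adverse events (SAEs) up to the one-month call in non-responders and through the applicable follow-up visit, which may be Month 6, in responders. The SAP compares deaths as percentages by arm with a chi-squared or Fisher test, and "adverse events causing treatment discontinuation and serious adverse events will be analyzed in the same manner". It states no cut-off date and no person-time.

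**The concern.** Responder status at EOT is an outcome of treatment, and here it is the primary outcome. If the arms have different response rates, or if different kinds of patients respond, the two responder groups are no longer comparable as randomised. A follow-up contrast between them mixes how long benefit lasts with who responded in each arm.

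Month 1 is the only follow-up point scheduled in both response groups, so it is the one place after EOT where the arms could be compared as randomised. The plan does not use it that way. Aim 3 promises the relative impact on quality of life over six months, but after EOT the QOLS exists only in responders.

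For SAEs, the arm with more responders is observed for longer on average. A crude percentage then counts slightly against that arm even when the underlying risk is equal.

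**Working it through.** **1. Who is in the follow-up model.** The protocol synopsis expects 60% of 400 = 240 responders, of whom 192 complete follow-up (192/240 = 80%). Both figures reproduce. The responder model therefore leaves out 400 - 240 = 160 randomised patients by design. At the SAP's planning rates (ECT 50%, ketamine 55%), responders number 100 + 110 = 210, and 190 are left out.

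**2. Size of the selection effect.** The documents give no correlation, so r is an assumption. Take a normal prognosis score (SD 1) with correlation r = 0.5 to 0.7 to a latent response score, and no treatment effect at follow-up. With response rate p and a = Phi^-1(p), write lam = phi(a)/p. Then:

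- mean among responders = r x lam
- variance among responders = 1 - r^2 x lam x (lam + a)

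lam is 0.798 at 50%, 0.720 at 55% and 0.644 at 60%. The bias is r times the difference in lam, and it runs against the arm with more responders. The response gaps of 5 and 10 points are those in the SAP's Sample size justification. Responder numbers use 80% completion: 200 x 0.50 x 0.8 = 80, 200 x 0.55 x 0.8 = 88 and 200 x 0.60 x 0.8 = 96.

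| Response | r | Bias (SD) | SE (SD) | Bias/SE |
|---|---|---|---|---|
| 50% vs 50% | any | 0 | | 0 |
| 50% vs 55% | 0.5 | 0.039 | 0.142 | 0.28 |
| 50% vs 55% | 0.7 | 0.055 | 0.129 | 0.43 |
| 50% vs 60% | 0.5 | 0.077 | 0.139 | 0.55 |
| 50% vs 60% | 0.7 | 0.108 | 0.127 | 0.85 |

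This is an unadjusted contrast, not the exact planned mixed model. In simulation under the same kind of model, the contrast pooling both response groups was 0.

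**3. Size of the SAE effect.** Assume the same hazard h in both arms and both response groups, and T = 0.75 months of treatment. Non-responders are observed for 1.75 months and responders for up to 6.75 months. At h = 0.02 per month:

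- non-responders: 1 - exp(-0.035) = 3.44%
- responders: 1 - exp(-0.135) = 12.63%
- difference: 9.19 points

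Multiplied by the response gap, the spurious difference between arms is 0.05 x 9.19 = 0.46 points, or 0.10 x 9.19 = 0.92 points. These are upper limits. If only 80% of responders go on to Month 6 and the rest stop at Month 1, they become 0.37 and 0.74. They are zero if all responders stop at Month 1. For h = 0.01 to 0.04 the upper limits are 0.24 to 0.85 and 0.48 to 1.69 points. The SE of the difference at 200 per arm and h = 0.02 is about 2.6 to 2.8 points.

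**4. Limits of a pooled Month 1 comparison.** Phone assessment coincides with non-response. An assumed mode effect of 0.25 to 0.5 SD would shift the pooled contrast by 0.05 x 0.25 = 0.013 to 0.05 x 0.5 = 0.025 SD at a 5-point gap, and by 0.025 to 0.05 SD at a 10-point gap. If planned attrition (10% in Protocol 9, 15% in the SAP) means patients with no EOT score, 40 to 60 of 400 have no scheduled Month 1 contact.

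**The case against.** **What stands.** The responder-only schedule is a design choice, and durability among responders is a legitimate question. Follow-up treatment is naturalistic, and no follow-up hypothesis or alpha is attached to the contrasts. The selection effect is small at the SAP's 5-point scenario, rests on assumed correlations, and disappears at equal response rates if similar patients respond. The synopsis itself plans about 120 responders in each arm. The remedy is imperfect too: at a 5-point gap, the possible mode shift is about a quarter to two thirds of the bias it removes.

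**What does not remove the point.** A non-responder model alongside the responder model still conditions on response. Neither model, nor the pair, gives a comparison as randomised.

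**Stronger readings that the documents do not support.**

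- A reader might infer that non-responder Month 1 data go unanalysed. The change summary mentions a model for them; what is absent is pooling.
- A reader might infer that the SAP has no other model that could reach follow-up. The vital-signs mixed model has no stated population, and neither does the regression for categorical outcomes, which could take in the 7-point PGI scales. The claim is secure for QIDS-SR-16 and the continuous scales that follow it.
- A reader might take Protocol 4.2's EOT baseline as evidence that adjustment makes responder selection worse. Under the model above, the EOT-adjusted arm contrast is the same in all patients as in responders. It comes from adjusting for a post-randomisation score, not from selecting responders.
- A reader might expect better precision from pooling. The two analyses estimate different quantities, so no such gain is claimed.

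**Conclusion.** The point holds and is minor to modest. For QIDS-SR-16 and the continuous scales that follow it, the follow-up arm comparison in the SAP body is restricted to EOT responders, and no comparison by randomised arm pooling both response groups is planned at Month 1, although four scales are scheduled there in both groups. Under the stated assumptions the bias stays below one standard error in every case examined. The primary endpoint is untouched.

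For Aim 3 the limit lies in data collection. Without QOLS in non-responders after EOT, later quality-of-life results cannot be read as the relative effect of the two treatments, and no analysis can recover that.

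The SAE point is a minor addition. A reader might infer that the safety comparison is seriously distorted, but at an assumed 2% monthly hazard the gap is at most 0.46 to 0.92 points, well inside its sampling error.

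**What to change.** 1. Add a secondary comparison at Month 1 by randomised arm, pooling responders and non-responders. Adjust QIDS, MADRS and PGI-S for the Visit 1 value, not the EOT score; analyse PGI-I without a baseline. State that any ECT or ketamine given clinically after EOT is included. Specify the imputation model for patients with no EOT score or no Month 1 contact, because the SAP's Missing data section gives none for secondary endpoints. One option is to extend the chained equations planned for the primary endpoint to include arm, baseline and acute-phase scores. Report the number imputed by arm. Add a sensitivity analysis that shifts phone scores over a stated range. Do not adjust for mode, since mode follows response status.
2. Describe responder-only follow-up results, including QOLS and cognition, as durability among responders and not as a randomised comparison. State that the all-randomised quality-of-life comparison for Aim 3 ends at EOT.
3. Compare SAEs and deaths from randomisation through the Month 1 contact in both response groups, using person-time or time to first event with censoring. Early stopping and the two-week visit window make a single fixed day unsuitable. Note that censoring may be informative, and report later responder events separately.

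The cost is SAP wording and a few tables, since the Month 1 scales and SAEs are already scheduled in both groups. The downsides to report are assessment mode tied to response, the two-week window either side of Month 1, clinical treatment after EOT, and some imputation.

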7.1.1 Screen Failures

If the patient fails to qualify for the study after signing the informed consent form, they will be considered a screen failure. Patients who screen fail and are not randomized will be eligible to rescreen at a later date. Patients should only be enrolled into the study once, therefore patients who have been randomized will not be eligible for future screening.

7.2 Baseline /Visit 1 (Randomization to occur as soon as possible, but within 1 week after eligibility is confirmed)

- Update Medical History
- Update Psychiatric Medication Log
- Update Somatic Therapies Log
- Clinical Psychiatric Evaluation
- Vitals (BP, heart rate, height, weight)
- Evaluation for AEs and SAEs

Questionnaires to be Completed Prior to Treatment

- Patient Rated Behavioral Scales
 - QIDS-SR-16 (to be completed first)
 - o SMCQ
 - o PGI-S
 - o QOLS
 - PRISE
 - o CPFQ
- Clinician Rate Behavioral Scales
 - MADRS
 - o CSSRS
 - YMRS
 - o CGI-S
- Cognitive Assessments
 - COWAT
 - HVLT-R
 - Stroop
 - NAART

ECT Procedure or Ketamine Infusion

Questionnaires to be Completed Post Treatment*

- CADSS
- o BPRS

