7.3 Treatment Visits (To occur over 3 to 5 weeks)

7.3.1 ECT Arm

Prior to each treatment, patients will be assessed if clinically appropriate for the treatment. Components of the evaluation for ECT will vary on a case-by-case basis. Each site will perform the following minimal set of assessments:

- Update Medical History
- Update Psychiatric Medication Log
- Update somatic therapies log
- Vitals (BP, heart rate, weight)
- Evaluation for Adverse Events or Serious Adverse Events
- Clinical Psychiatric Evaluation
- Patient and Clinician Rated Behavioral Scales (to be completed at Baseline/Visit 1, Visit 2, Visit 4, Visit 6, Visit 7, and Visit 9)

Prior to Treatment:

- Patient Rated Behavioral Scales
 - QIDS-SR-16 (To be completed first)
 - GSE-MY (Not completed at Baseline/Visit 1)
 - o SMCQ
 - o PGI-S & PGI-I (PGI-I not completed at Baseline/Visit 1)
 - o QOLS
 - o PRISE
 - o CPFQ
- Clinician Rated Behavioral Scales
 - o MADRS
 - o CSSRS
 - YMRS
 - CGI-S & CGI-I (CGI-I not completed at Baseline/Visit 1)
- Post Treatment (clinician rated)
 - o CADSS
 - o BPRS

^{*}Patients in the ECT arm will need to have a recovery period prior to completing the post treatment questionnaires.

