Eligibility Criteria	X											
Demographics	X											
Medical history	X		X	X	X	X	X	X	X	X	X	X
Urine pregnancy test	X											
Vitals (BP, heart rate, weight)			X	X	X	X	X	X	X	X	X	BP, HR
Randomization		X										
Psychiatric Evaluation	X		X	X	X	X	X	X	X	X	X	X
ECT			X	X	X	X	X	X	X	X	X	
Psychiatric Medication Log	X		X	X	X	X	X	X	X	X	X	X
Somatic Therapies Log	X		X	X	X	X	X	X	X	X	X	X
Evaluate for AEs/SAEs			X	X	X	X	X	X	X	X	X	X
Diagnostic Interview												
MINI 7.0.2	X											
Patient Rated Scales												
QIDS-SR-16			X	X		X		X	X		X	X

Schedule of Events (ECT Arm)

Visit	Screening (Maximum of 28 days)	Randomization (within 1 week after eligibility is confirmed)	(Up to 9 treatments over 3- 5 weeks)									EOT (within 3 days after last treatment)
			Baseline/ V1	V2	V3	V4	V ₅	V6	V7	V8	V9	
GSE-MY				X		X		X	X		X	X
SMCQ			X	X		X		X	X		X	X
PGI-S			X	X		X		X	X		X	X
PGI-I				X		X		X	X		X	X
QOLS			X	X		X		X	X		X	X
PRISE			X	X		X		X	X		X	X
CPFQ			X	X		X		X	X		X	X
Treatment Preference												X
Clinician Rated Scales												
MADRS	X		X	X		X		X	X		X	X
CSSRS			X	X		X		X	X		X	X
YMRS	X		X	X		X		X	X		X	X
BPRS*			X	X		X		X	X		X	X
CGI-S**			X	X		X		X	X		X	X
CGI-I**				X		X		X	X		X	X
CADSS*			X	X		X		X	X		X	X
Cognitive Assessments												
MoCA	X											X
COWAT			X			1						X
HVLT-R			X									X
Stroop			X									X
NAART			X									

^{*}CADSS and BPRS to be administered post treatment.
**CGI-S and CGI-I to be performed by psychiatrist.

Schedule of Events (Ketamine Arm)

Visit	Screening (Maximum of 28 days)	Randomization (within 1 week of confirmed eligibility)	Treatment Phase (Up to 6 treatments over 3-5 weeks)						EOT (within 3 days after last treatment)
			Baseline/V1	V2	V3	V4	V5	V6	
Informed consent	X								
Eligibility Criteria	X								
Demographics	X								
Medical history	X		X	X	X	X	X	X	X
Urine pregnancy test	X								
Vitals (BP, heart rate, , weight)			X	X	X	X	X	X	BP, HR
Randomization		X							
Psychiatric Evaluation	X		X	X	X	X	X	X	X
Ketamine Infusion			X	X	X	X	X	X	
Psychiatric Medication Log	X		X	X	X	X	X	X	X
Somatic Therapies Log	X		X	X	X	X	X	X	X
Evaluate for AEs /SAEs			X	X	X	X	X	X	X
Diagnostic Interview									
MINI 7.0.2	X								
Patient Rated Scales									
QIDS-SR-16			X	X	X	X	X	X	X

Schedule of Events (Ketamine Arm)

Visit	Screening (Maximum of 28 days)	Randomization (within 1 week of confirmed eligibility)		EOT (within 3 days after last treatment)					
			Baseline/V1	V2	V3	V4	V5	V6	
GSE-MY				X	X	X	X	X	X
SMCQ			X	X	X	X	X	X	X

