ELEKT–D: Electroconvulsive therapy (ECT) vs. ketamine in patients with treatment resistant depression (TRD)

Statistical Analysis Plan

Version 2.0 07/01/2022

ELEKT-D is an open label, multi-center clinical trial to compare electroconvulsive therapy (ECT) with ketamine (KET) in patients with treatment resistant depression (TRD). The specific study aims include:

- Aim 1: to investigate the comparative effectiveness of ECT and ketamine on measures of depression.
- Aim 2: To investigate the relative impact of ECT and ketamine on measures of memory and cognitive function.
- Aim 3: To investigate the relative impact of ECT and ketamine on patient reported QoL measures after acute treatment and at follow-up over six months.

Table 1 below lists the primary, secondary and safety endpoints measured from the study participants. More details and the measurement schedules of these endpoints are described in the study protocol.

Analysis of baseline characteristics. The analysis will be based on the randomized population (i.e., all participants randomized). Participant characteristics at baseline will be summarized as descriptive statistics (mean, standard deviation [SD], median, inter-quartile range, or range for continuous data, and count and percentage for categorical data). The baseline characteristics will be compared between the two study groups using the t-test, the Wilcoxon rank sum test, or the chi-squared test as appropriate.

Analysis of primary endpoint. The primary endpoint of the trial is treatment response, which is defined as $a \ge 50\%$ decrease in QIDS-SR-16 scores from the baseline visit/visit 1 to the end of treatment visit in the acute phase. The study hypothesis is that the response rate of ketamine is non-inferior to ECT with a margin of -10%, that is,

$$H_0: P_k - P_e \le -10\%$$
 vs. $H_1: P_k - P_e \ge -10\%$

where P_k represents the response rates in the ketamine group, and P_e represents the response rate in the ECT grou; H_0 and H_1 denote the null and alternative hypotheses, respectively. The primary endpoint of treatment response will be summarized as proportions, along with 95% confidence intervals, for each treatment group. The Farrington-Manning score test will be then used to compare the response rates between ECT and KET at an inferiority margin of -10% (ketamine minus ECT) and a one-sided type I error of 0.025. The difference of the two response rates will be also reported with the 95% confidence interval.

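### Must the SAP exclude CADSS and BPRS from its change-from-baseline model in the acute phase, given that neither scale has a pre-treatment score?

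*SAP*

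**What the plan says.** SAP, Analysis of secondary endpoints, first describes a mixed model for the QIDS-SR-16 score in the acute phase, with time, arm, their interaction and site, and arm contrasts at each visit. The within-patient covariance is chosen by information criterion from compound symmetric, AR1, Toeplitz and unstructured forms. It then describes a model of the same form for responders in follow-up. Next comes a change model, with no phase named, which "will include the score changes as the dependent variable and further include the baseline QIDS-SR-16 score as a covariate". The remaining scales are covered by one sentence: "For the other continuous secondary endpoints measured longitudinally, their analyses will follow the analysis of the QIDS-SR-16 score". The examples that follow name MADRS and YMRS but not CADSS or BPRS. SAP Table 1 lists both as secondary endpoints.

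The SAP identifies baseline with Visit 1 only when it defines the primary endpoint, as a decrease "from the baseline visit/visit 1 to the end of treatment visit in the acute phase".

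The Protocol is clear on timing. Section 4.2: "All scales (except CADSS and BPRS) will be administered prior to treatment". Section 7.2 puts CADSS and BPRS at Visit 1 under the heading "Questionnaires to be Completed Post Treatment", with the footnote "Patients in the ECT arm will need to have a recovery period prior to completing the post treatment questionnaires". Both Schedules of Events repeat the rule: "CADSS and BPRS to be administered post treatment". Neither scale is among the screening assessments in section 7.1. For Months 1, 3 and 6, section 4.2 makes the EOT visit the baseline.

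**The concern.** For every other scale completed at Visit 1, that score precedes treatment and is a true baseline. For CADSS and BPRS, the score in the Baseline/V1 column follows the first treatment. An analyst who carried the QIDS-SR-16 change model over mechanically would subtract a post-randomisation score and also adjust for it.

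The Protocol's Background section names dissociation and psychotic-like symptoms as ketamine effects, and these are what CADSS and BPRS measure. Part of the acute effect would then be removed from the later comparison, in favour of the arm with the larger first-session effect. At EOT, when symptoms may have resolved, the model could show a difference where none exists. The comparison at stake is tolerability on two scales in an open-label trial.

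**Working it through.** **What the text requires.** The problem arises only if four things hold together.

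| Condition | What the documents say |
|---|---|
| The change model is used in the acute phase | Not stated; its sentence directly follows the responder follow-up model |
| It is used for CADSS and BPRS | Not stated; the carry-over sentence could mean the score model, the change model or both |
| Visit 1 is their baseline | Stated only for the primary endpoint; follow-up uses EOT, where both scales are scored (Protocol 7.4) |
| The arms differ on them at Visit 1 (D1 not zero) | No values given; the Background calls such symptoms infrequent at sub-anesthetic doses and quickly reversed |

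**Size if all four hold.** The plan states no figure to reproduce, so D1, the correlations and the SDs below are assumptions. Let D_t be the true arm difference at visit t, and b the within-arm slope of the visit-t score on the Visit 1 score, b = rho × SD_t / SD_1. With change as outcome and the Visit 1 score as covariate, the arm contrast is

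(D_t - D1) - (b - 1) × D1 = D_t - b × D1.

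The shift is -b × D1, and it is zero if D1 is zero.

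*Check at one later visit.* With D1 = D_t = 1 SD and equal SDs, the contrast should be 1 - rho, that is 0.70, 0.50 and 0.30 for rho 0.3, 0.5 and 0.7. A simulation of 200,000 patients gave 0.701, 0.504 and 0.299. The plain score comparison gave 0.997 to 1.003, against a true value of 1.

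*All acute visits together.* The change model as written has one baseline coefficient, so a single pooled b applies at every visit. After Visit 1 each arm has five post-session assessments and EOT (ECT: V2, V4, V6, V7, V9, EOT; ketamine: V2 to V6, EOT). Take full reversal by EOT: no arm difference there and no correlation with Visit 1. Let the session scores have equal SDs and a common correlation rho, with D1 = 1 SD. The true EOT contrast is 0, so the false contrast is -b.

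Under compound symmetry the pooled slope is the mean of the six visit slopes, (5 × rho + 0)/6 = 0.25, 0.42, 0.58. Under an unstructured covariance it is the b that minimises the log-determinant of the residual covariance of the six later scores.

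| EOT SD / session SD | Pooled b, unstructured (rho 0.3 / 0.5 / 0.7) | Pooled b, compound symmetric |
|---|---|---|
| 0.25 | 0.045 / 0.076 / 0.13 | 0.25 / 0.42 / 0.58 |
| 0.5 | 0.13 / 0.21 / 0.34 | 0.25 / 0.42 / 0.58 |
| 1 | 0.22 / 0.37 / 0.55 | 0.25 / 0.42 / 0.58 |

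*Which structure the SAP would select.* At its 346 patients (173 per arm) and an SD ratio of 0.25, expected BIC is 1008 for unstructured against 1459 for compound symmetric at rho 0.3, 638 against 1057 at 0.5, and -10 against 444 at 0.7. Unstructured also wins at a ratio of 0.5. At a ratio of 1, AIC still selects it, while BIC prefers a simpler form at rho 0.3. In 300 simulated trials at ratio 0.25 with unstructured covariance, the EOT contrast was -0.05, -0.08 and -0.13 (Monte Carlo SE 0.002). The last-session contrast was 0.95, 0.93 and 0.86, against a true 1.

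**The score model.** It treats Visit 1 as the first outcome and neither subtracts nor adjusts for it. Its contrast at each visit is D_t, and EOT is already estimated apart from the session visits.

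**The case for a change.** The best case for a change is that the mistake would give no warning. GSE-My, PGI-I and CGI-I also lack a Visit 1 score, but there the change model fails visibly because the value does not exist. CADSS and BPRS have a value filed under the baseline visit, so the model would run. The list of examples does not exclude them: it is illustrative, and YMRS, a mania scale, already lies outside the three domains it names. The carry-over sentence is also the only specific place in the SAP for their acute-phase longitudinal data. One sentence would settle the matter.

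The silence is real, the algebra is right, and a clarifying line would be cheap. But that line would only record which of two planned models applies. It would add no analysis, and the sound model is the one the SAP describes first. The Protocol states the post-treatment timing in section 4.2, in section 7.2 and in both schedules, so an analyst preparing these scales will meet it. The arm difference in post-session timing caused by the ECT recovery period would remain under either model.

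**Conclusion.** This is missing detail that a competent analyst fills correctly; the plan does not prescribe a wrong analysis. CADSS and BPRS have no pre-treatment score, and the SAP does not say where its change model stops. The faulty analysis nevertheless needs all four conditions in the table, and the documents require none of them.

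If it were run, the false EOT difference would be about 0.05 to 0.13 of D1 with an EOT SD a quarter of the session SD, and 0.13 to 0.34 with half. It approaches 0.25 to 0.58 only if EOT and session SDs are equal or compound symmetry is imposed. Equal SDs are hard to reconcile with full reversal, and compound symmetry loses the SAP's own covariance selection at SD ratios of 0.25 and 0.5. These figures rest on assumed correlations, SDs and a full-reversal pattern, and they vanish if D1 is zero.

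The primary endpoint, MADRS response and the score model are unaffected, and follow-up has EOT as its baseline. No change to the plan follows.
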